#### 6.4.5. Main outcome

Non responders will be those patients not achieving a reduction in HBI of at least 2 points from baseline for CD, and a decrease in the PMS of at least 2 points for UC.. In the cases where these indexes are not available, clinical response will be evaluated according to physician criteria at short term (10 weeks after starting the anti-TNF) and at long term (at least 6 months after starting the anti-TNF). Primary non-responders (PNR) were defined as patients with no clinical response at short term. Loss of response (LOR) was defined as loss of the effect of the drug along the follow up in a patient with initial response.

Reasons to stop the drug will be classified as follows: PNR, LOR, side effects (SE), remission and other.

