7. EFFICACY ASSESSMENT

7.1. Efficacy Assessment; general considerations

Non responders will be those patients not achieving a reduction in HBI of at least 2 points from baseline for CD and a decrease in the PMS of at least 2 points for UC.

In the cases where these indexes are not available, clinical response will be evaluated according to physician criteria at short term (10 weeks after starting the anti-TNF [*primary response and primary non-response*]) and at long term (at least 6 months after starting the anti-TNF [*primary response maintenance and loss of response*]).

We will calculate the following variables:

- **Lack response during the induction phase (primary non response):** Those patients who 10 weeks after starting the anti-TNF not achieving a reduction in HBI of at least 2 points from baseline for CD and a decrease in the PMS of at least 2 points for UC. In the cases where these indexes are not available, clinical response will be evaluated according to physician criteria at short term (*primary response and primary non-response*).
- **Loss of response during the maintenance phase (secondary loss of response):** Those patients who at least 6 months after starting the anti-TNF not achieving a reduction in HBI of at least 2 points from baseline for CD and a decrease in the PMS of at least 2 points for UC. In the cases where these indexes are not available, clinical response will be evaluated according to physician criteria at short term (*primary response maintenance and loss of response*).

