7.2. Primary efficacy endpoint

- **Primary endpoint:** Evaluate the impact of the co-morbidities profile in IBD patients on treatment response to biological therapy.

The analysis that will be performed to answer the objective will be the following:

In order to determine the level of correlation between the co-morbidities profile and treatment response, adjusting for sociodemographic and clinical profile of patients, two logistic regression models will be conducted. The dependent variable of the models will be the **lack of response during the induction phase and the loss of response during the maintenance phase**. In both models independent variables will include all comorbidities, as well as sociodemographic and clinical variables as covariates.

- The following potential variables will be considered for the analysis:
 - Crohn's Disease or Ulcerative Colitis.
 - Myocardial Infarction (yes/no).
 - Congestive Heart Failure (yes/no).
 - Peripheral Vascular Disease (yes/no).
 - Cerebrovascular Disease (yes/no).
 - Dementia (yes/no).
 - Chronic Obstructive Pulmonary Disease (yes/no).
 - Connective Tissue Disease (yes/no).
 - Peptic Ulcer Disease (yes/no).
 - Mild Chronic Hepatopathy (yes/no).
 - Diabetes Mellitus (yes/no).
 - Hemiplegic (yes/no).
 - Moderate-Severe Chronic Kidney Disease (yes/no).
 - Diabetes with lesions in target organs (yes/no).
 - Solid Tumor (yes/no).
 - Leukemia (yes/no).
 - Lymphoma (yes/no).

- Moderate-Severe Chronic Hepatopathy (yes/no).
 - Solid tumor with metastases (yes/no)
 - Acquired immunodeficiency syndrome (AIDS) (yes/no).
 - Gender.
 - Race (caucasian, asiatic, latin, black, other).
 - Level of education (uneducated, primary education, secondary education, university education).
 - Working status (student, self-employed, employed by other, retired, housework, unemployed, temporarily unable to work, permanently unable to work, other).
 - Smoking habits (non-smoker, ex-smoker and smoker).
 - Alcohol abuse (yes/no).
 - Time from diagnostic of disease.
 - Disease location.
 - Discontinuation the biological treatment (yes/no)
- Each one of the variables will be compared between the subjects with primary non-response vs primary response and primary response maintenance vs loss of response and those variables whose p-value is lower than 0.1 are considered potential variables for performing a logistic regression analysis.

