- Non severe (Remission <5; Mild disease 5-7; Moderate disease 8-16)
- Severe disease >16

Partial Mayo Index Score

- Non severe (Remission = 0-1; Mild Disease = 2-4; Moderate Disease = 5-7)
- Severe Disease =8-9

We will compare the percentage of patients reporting each co-morbidity between IBP severe or non-severe using Chi-Square.

A logistic regression analysis will be performed, in which **IBP severe or non-severe at baseline** will be used as the dependent variable and patient disease (CD or UC) and different comorbidities variables will be used as independent variables, yielding the following results: Odds Ratio, 95%CI, p-value, sensitivity and specificity.

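### SAP 7.1 defines loss of response by the primary non-response test, without limiting it to initial responders or looking at the response they reached

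*SAP*

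**What the plan says.** Protocol 6.4.5 gives the concept: "Loss of response (LOR) was defined as loss of the effect of the drug along the follow up in a patient with initial response". It gives no score rule for LOR. Its only score rule is the response criterion, a fall of at least 2 points from baseline in HBI (CD) or PMS (UC).

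SAP 7.1 turns this into two variables:

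- For primary non-response the text is: "Those patients who 10 weeks after starting the anti-TNF not achieving a reduction in HBI of at least 2 points from baseline for CD", with the matching PMS test for UC.
- For secondary loss of response the text is: "Those patients who at least 6 months after starting the anti-TNF not achieving a reduction in HBI of at least 2 points from baseline", again with the matching PMS test.

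The two definitions differ only in timing. The LOR text does not mention initial response, the week-10 score or the activity level at follow-up. The physician's view is a fallback only: "In the cases where these indexes are not available, clinical response will be evaluated according to physician criteria".

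SAP 7.2 then compares "primary response maintenance vs loss of response" and models LOR as the second of the two primary outcomes. SAP 7.3 repeats the extraintestinal-manifestation model with LOR as outcome, and supplies the activity bands used below: "Non severe (Remission <5; Mild disease 5-7; Moderate disease 8-16" and "Severe disease >16" for HBI, and "Non severe (Remission = 0-1; Mild Disease = 2-4; Moderate Disease = 5-7" for PMS, with severe at 8-9.

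**The concern.** Two kinds of patient can land in the wrong group.

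1. **Never responded.** A patient who fails the test at week 10 and still fails it at 6 months or later satisfies the LOR text, although there was no response to lose.
2. **Responded, then relapsed.** The late score is compared with the pre-treatment score, so a large initial gain works as a cushion. The larger the gain, the more of it must be lost before LOR is counted.

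LOR is the outcome of one primary model and one secondary model. The second error grows with the baseline score, and baseline HBI/PMS is not in the SAP 7.2 list of candidate variables. A secondary objective asks whether comorbidity is related to severity. If it is, the LOR odds ratios would partly reflect how far a patient could fall in score, not loss of drug effect.

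**Working it through.** **Plan's own figure.** Protocol 7.1: 10 events per variable × 10 variables / 0.50 = 200 per disease. This reproduces, and it does not depend on how LOR is defined.

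**The rule in symbols.** Let b be the baseline score, r the week-10 score and l the follow-up score. Initial response means r ≤ b − 2. SAP LOR means l > b − 2, that is l ≥ b − 1. With gain G = b − r, LOR needs l − r ≥ G − 1:

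- G = 2: 1 point lost (50% of the gain)
- G = 6: 5 points lost (83%)
- G = 10: 9 points lost (90%)

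**Records applied literally** (patient still on the first biologic, index available):

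| Index | Baseline, week 10, follow-up | Bands, week 10 to follow-up | Fall from baseline | SAP label |
|---|---|---|---|---|
| PMS | 9, 1, 7 | remission to moderate | 2 | maintained |
| HBI | 18, 4, 15 | remission to moderate | 3 | maintained |
| PMS | 4, 2, 3 | mild to mild | 1 | LOR |
| PMS | 7, 7, 7 | moderate, never responded | 0 | LOR |

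**How bad can a maintained state be?** It needs l ≤ b − 2.

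- UC, moderate (PMS 5-7): baseline of at least 5 + 2 = 7.
- UC, severe (PMS 8-9): baseline of at least 8 + 2 = 10, which is impossible on a scale that stops at 9.
- CD, moderate (HBI 8-16): baseline of at least 8 + 2 = 10.
- CD, severe (HBI 17 or more): baseline of at least 17 + 2 = 19.

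**Counting score pairs.** These are possible patterns, not patient frequencies.

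- PMS, baseline 5-9, follow-up from 5 up to baseline: 15 pairs, of which 6 count as maintained: (7,5), (8,5), (8,6), (9,5), (9,6), (9,7).
- HBI, baseline 8-20, follow-up from 8 up to baseline: 91 pairs, of which 66 count as maintained. Only 3 of these are severe: (19,17), (20,17), (20,18).

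**Simulation.** The documents give no score distributions, so these are assumptions: baseline PMS about N(6.5, 1.5) or HBI about N(10, 3.5), remission or mild disease after induction, and relapse to the moderate or severe band. The share of such relapsers filed as maintained is:

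| Share of gain lost | UC | CD |
|---|---|---|
| 50-100% | 26% | 49% |
| 75-100% | 4% | 23% |

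Among the misfiled CD relapsers, about 0.5% (50-100% lost) to 2% (75-100% lost) were severe.

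**Never-responders, upper bound.** Protocol section 4 cites up to 30% primary non-response to anti-TNF, and Protocol 7.1 plans on 50% non-response. In 200 patients that is 200 × 0.30 = 60 to 200 × 0.50 = 100 who could meet the LOR text if all still failed the test later. The documents do not say how many would have a later reading.

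**The case against.** The strongest reply is that the rule is coherent. The protocol defines response as a 2-point fall from baseline and gives no other score rule, so no longer meeting that criterion is a fair reading of losing response. That stands: a reader might infer that anchoring to baseline contradicts the protocol, and the documents do not go that far. The clear departure from Protocol 6.4.5 is the missing restriction to initial responders. On that, the group labels in SAP 7.2 suggest the restriction was intended, but the SAP 7.1 definition that creates the variable does not contain it.

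A reader might also infer that severe relapses are routinely filed as maintained. They are not: this is impossible in UC and needs a baseline HBI of at least 19 in CD.

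Anchoring to the week-10 score instead has problems of its own. Protocol 6.4.4 lists activity scores only at the start of the reference period and at the study visit. Such a rule also over-calls. With LOR as a rise of at least 2 points to PMS 2 or more, PMS 9, 0, 2 becomes LOR with a 7-point improvement kept. Of the 120 PMS patterns with initial response, a rise of at least 2 and follow-up no worse than baseline, 20 would be LOR while still at least 4 points below baseline.

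Finally, some relapses will be visible elsewhere, because LOR is recorded as a reason for stopping (Protocol 6.4.5, SAP 6.1) and intensification is described. Neither feeds the SAP 7.1 variable, and no precedence is stated if they disagree with the index. This softens the problem without curing it.

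**Conclusion.** The point holds as a definitional weakness in a primary outcome and should be corrected. The SAP text lets persistent non-responders qualify as LOR, and lets initial responders with a high baseline return to moderate disease (rarely severe, in CD only) while labelled as maintained. Both follow directly from the wording and the SAP's own bands wherever the index is available; otherwise the physician decides.

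The size is not known. The 4-26% (UC) and 23-49% (CD) are illustrations that rest wholly on the assumed distributions and apply only to relapsers already back in an active band. Changing the assumed loss of gain alone moves UC from 26% to 4%. It is tempting to conclude that the LOR odds ratios are biased. The documents do not establish that, because they do not show that comorbidity or extraintestinal manifestations are related to baseline score.

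**What to change.** In SAP 7.1 and 7.2:

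1. Restrict the LOR variable, and every model that uses it, to initial responders, identified at week 10 by index or physician judgement.
2. Among them, count LOR when the follow-up index no longer meets the 2-point criterion, **or** when the patient is back in the moderate or severe band of SAP 7.3. This uses the study-visit score already collected. Where a week-10 index shows that the patient never left that band, apply the 2-point criterion alone.
3. As sensitivity analyses, run a version anchored to the week-10 value where the chart has it, and report the current baseline-anchored rule.
4. Add baseline HBI/PMS to the candidate covariates in SAP 7.2.
5. State which source takes precedence when the index, the physician's judgement and LOR as a stopping reason disagree.

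Under this rule PMS 9, 1, 7 and HBI 18, 4, 15 become LOR, the never-responder leaves the model, and PMS 4, 2, 3 remains LOR.

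The cost is SAP wording and a little more analysis. Some partial relapses with retained benefit will be counted as LOR. So will some responders who stayed in the moderate band throughout, where no week-10 index exists to show it. Restricting the model to initial responders also reduces its sample, so the number of variables must follow the 10-per-category rule in Protocol 7.4.

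### SAP 7.1 ties the fallback assessment for loss of response to short term (10 weeks) instead of long term (at least 6 months), against its own general rule and Protocol 6.4.5

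*SAP*

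**What the plan says.** SAP 7.1 opens with a general rule for patients whose HBI or PMS is not available. The physician's judgement is used at two times. The first is "short term (10 weeks after starting the anti-TNF [*primary response and primary non-response"; the second is "at long term (at least 6 months after starting the anti-TNF [*primary response maintenance and loss of response". Protocol 6.4.5 gives the same two times: "at short term (10 weeks after starting the anti-TNF) and at long term (at least 6 months after starting the anti-TNF".

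SAP 7.1 then lists the two variables to be calculated. The PNR bullet sends patients without an index to the short-term judgement: "clinical response will be evaluated according to physician criteria at short term (*primary response and primary non-response". The LOR bullet starts with an index rule at the later time, "Those patients who at least 6 months after starting the anti-TNF not achieving a reduction in HBI of at least 2 points", but its fallback reads "clinical response will be evaluated according to physician criteria at short term (*primary response maintenance and loss of response".

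Protocol 6.4.5 also defines the concept: "Loss of response (LOR) was defined as loss of the effect of the drug along the follow up in a patient with initial response".

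**The concern.** The LOR bullet pairs the long-term outcome categories with the short-term time point. It therefore disagrees with the general rule above it, with its own index-based half, and with Protocol 6.4.5. The only meaning either document gives to short term is 10 weeks. That is when initial response is established, so it is too early to judge whether a response was kept or lost.

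The variable carries weight. LOR is the outcome of one of the two primary logistic models and of the univariate screen at p < 0.1 that feeds it (SAP 7.2). It is also the outcome of the repeated extraintestinal-manifestations model (SAP 7.3), and it supplies tables 14.3.1.3, 14.3.1.4 and 14.3.2.2. The fallback is a path that can be used: the study is retrospective, Protocol 6.4.4 takes clinical variables from records where available, and both documents foresee missing indices.

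**Working it through.** **Step 1. The rules side by side.**

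| Place | Outcome named | Time for the index | Time for the physician fallback |
|---|---|---|---|
| SAP 7.1, general rule | primary response / non-response | none stated | short term, 10 weeks |
| SAP 7.1, general rule | maintenance / loss of response | none stated | long term, at least 6 months |
| SAP 7.1, PNR bullet | primary response / non-response | 10 weeks | short term |
| SAP 7.1, LOR bullet | maintenance / loss of response | at least 6 months | **short term** |
| Protocol 6.4.5 | clinical response; PNR tied to short term, LOR to follow-up | none stated | 10 weeks and at least 6 months |

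The fallback in the LOR bullet is the only entry out of line. Its sentence matches the PNR sentence except for the bracketed categories.

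**Step 2. What the literal rule yields for a patient without an index.** At 10 weeks the patient is either a responder or a non-responder.

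- *Reading A: initial response required, as in Protocol 6.4.5.* Non-responders are PNR and are not candidates for LOR. Responders have not yet had the follow-up in which to lose response. The group contributes no LOR events.
- *Reading B: no initial response required; the SAP bullet states no such condition.* The 10-week non-responders are coded as LOR, and later losses among 10-week responders are not captured.

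**Step 3. The plan's own figure.** Protocol 7.1 allows 10 variables, asks for 10 events per variable and assumes 50% response: 10 × 10 / 0.50 = 200 per disease. This reproduces the stated figure, and the wording conflict does not change it.

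**Step 4. Size, as an illustration.** Inputs:

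- N = 200 per disease (Protocol 7.1).
- PNR = 30%, the upper figure in the protocol's background section, so responders = 200 × 0.70 = 140.
- L, the LOR rate among responders: not in the documents; assumed 20%, 35% or 50%.
- m, the share without an index: not in the documents; assumed 10% to 70%, and taken as unrelated to response.

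With the long-term fallback, LOR events = 140 × L. Under Reading A, events = 140 × L × (1 − m). Under Reading B, primary non-responders without an index who are coded as LOR = 200 × 0.30 × m.

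| | Long-term fallback | m = 10% | m = 30% | m = 50% | m = 70% |
|---|---|---|---|---|---|
| Reading A, L = 20% | 28 | 25.2 | 19.6 | 14.0 | 8.4 |
| Reading A, L = 35% | 49 | 44.1 | 34.3 | 24.5 | 14.7 |
| Reading A, L = 50% | 70 | 63.0 | 49.0 | 35.0 | 21.0 |
| Reading B, miscoded PNR | 0 | 6 | 18 | 30 | 42 |

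Protocol 7.4 asks for 10 patients per variable in each response category. At L = 35%, the number of variables the LOR model can carry is 4 with the long-term fallback. Under Reading A it is 4, 3, 2 and 1 across the four values of m. If CD and UC are pooled (SAP 7.2 lists disease type as a candidate variable), all counts double. The relative loss under Reading A is m itself, whatever L or N.

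Reading B counts only the fallback group. The index-based half of the bullet also omits the initial-response condition; that is a separate gap and is not included here.

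**The case against.** The strongest reply is that this is a drafting slip whose meaning can be recovered. The bullet is headed as a maintenance-phase outcome, its index rule is set at 6 months, and its bracketed categories are attached only to the long-term judgement in the general rule. A careful programmer would probably read it as long term. This is a fair account of how the phrase arose, and it limits the severity. It does not settle the matter, because this bullet is the derivation specification and the choice should not rest on the programmer's inference.

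A reader might infer something stronger: that LOR cannot be observed in patients without an index, that every LOR event coded in them is a primary non-responder, and that the LOR model therefore just repeats the PNR model. The documents do not support this:

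- The second and third parts need Reading B. Under the protocol's definition these patients have no coded events rather than wrong ones, and no text tells the programmer to relabel the 10-week categories as maintenance and loss.
- LOR is also recorded as a reason for stopping the drug (Protocol 6.4.5, SAP 6.1), with date and reason collected (Protocol 6.4.4). Late losses that led to stopping are in the data, although the derivation does not use them.
- Disease activity is planned at the start of biological treatment and at the study visit (Protocol 6.4.4). That visit should fall well beyond 6 months for most patients, so the fallback may be needed less often for LOR than for the 10-week outcome.
- The share without an index is not stated, so no particular size can be claimed.

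**Conclusion.** The contradiction is explicit in the current SAP text and sits in the working definition of one of the two primary dependent variables. It should be corrected. It is probably a copied sentence rather than a deliberate analysis choice.

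The effect is confined to patients without HBI or PMS. In that group the literal rule gives either no LOR events or 10-week non-responders coded as LOR, depending on whether an initial response is required. In the illustration the loss of LOR events equals the share without an index (10% to 70%), and the miscoding is 6 to 42 patients per disease. Both ranges rest on assumed inputs and show only the direction and scale. The sample size of 200 per disease is unaffected.

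**What to change.** In the LOR bullet of SAP 7.1, replace the words *at short term* with "at long term (at least 6 months after starting the anti-TNF" and close the bracket. The bullet then agrees with the general rule in SAP 7.1 and with Protocol 6.4.5. Make the matching change in the derivation code.

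Also state in the SAP which collected variable supplies the long-term physician assessment. The variable list in Protocol 6.4.4 includes a physician's global assessment of disease activity, but it shows no separate response item at 10 weeks or at 6 months or later, so the source has to be confirmed.

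The wording change costs one phrase and adopts a rule that both documents already state. It asks for no new data. Whether the assessment was in fact recorded cannot be judged from the documents.

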7.2. Primary efficacy endpoint

- **Primary endpoint:** Evaluate the impact of the co-morbidities profile in IBD patients on treatment response to biological therapy.

The analysis that will be performed to answer the objective will be the following:

In order to determine the level of correlation between the co-morbidities profile and treatment response, adjusting for sociodemographic and clinical profile of patients, two logistic regression models will be conducted. The dependent variable of the models will be the **lack of response during the induction phase and the loss of response during the maintenance phase**. In both models independent variables will include all comorbidities, as well as sociodemographic and clinical variables as covariates.

- The following potential variables will be considered for the analysis:
 - Crohn's Disease or Ulcerative Colitis.
 - Myocardial Infarction (yes/no).
 - Congestive Heart Failure (yes/no).
 - Peripheral Vascular Disease (yes/no).
 - Cerebrovascular Disease (yes/no).
 - Dementia (yes/no).
 - Chronic Obstructive Pulmonary Disease (yes/no).
 - Connective Tissue Disease (yes/no).
 - Peptic Ulcer Disease (yes/no).
 - Mild Chronic Hepatopathy (yes/no).
 - Diabetes Mellitus (yes/no).
 - Hemiplegic (yes/no).
 - Moderate-Severe Chronic Kidney Disease (yes/no).
 - Diabetes with lesions in target organs (yes/no).
 - Solid Tumor (yes/no).
 - Leukemia (yes/no).
 - Lymphoma (yes/no).

- Moderate-Severe Chronic Hepatopathy (yes/no).
 - Solid tumor with metastases (yes/no)
 - Acquired immunodeficiency syndrome (AIDS) (yes/no).
 - Gender.
 - Race (caucasian, asiatic, latin, black, other).
 - Level of education (uneducated, primary education, secondary education, university education).
 - Working status (student, self-employed, employed by other, retired, housework, unemployed, temporarily unable to work, permanently unable to work, other).
 - Smoking habits (non-smoker, ex-smoker and smoker).
 - Alcohol abuse (yes/no).
 - Time from diagnostic of disease.
 - Disease location.
 - Discontinuation the biological treatment (yes/no)
- Each one of the variables will be compared between the subjects with primary non-response vs primary response and primary response maintenance vs loss of response and those variables whose p-value is lower than 0.1 are considered potential variables for performing a logistic regression analysis.
 - For the comparison of the variables between subjects, the following criteria will be considered: dichotomous or categorical variables will be compared between the two groups using the Chi-squared test. Continuous variables will be compared between the two groups using the Student's T-test for independent samples.
- The logistic regression models will be assessed and the results will be submitted for any statistically significant model, providing the following results: Odds Ratio, 95%CI, p-value, sensitivity and specificity. The models will be assessed using stepwise automatic variable Wald entry (backward and forward) techniques and entry also assessing the specificity and sensitivity of the final model.

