#### **7.4. Assessment of the primary objective: Evaluate the impact of the co-morbidities profile in IBD patients on treatment response to biological therapy**

In order to determine the level of correlation between the co-morbidities profile and treatment response, adjusting for sociodemographic and clinical profile of patients, two logistic regression models will be conducted. The dependent variable of the models will be the lack of response during the induction phase (primary non response) and the loss of response during the maintenance phase (secondary loss of response) (see section 6.4.6). In both models independent variables will include all comorbidities included in the study, as well as sociodemographic and clinical variables as covariates. The maximum number of independent variables included in the model will be defined according to the number of patients per response category in the dependent variable. The maximum number of variables will be defined to ensure a minimum of 10 patients per independent variable and response category in the dependent one.

Depending on the volume of patients that have discontinued a biological treatment and started treatment with a different biologic during the reference period, this sample may be separately analyzed.

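### SAP 7.2 spreads the primary objective over up to 38 unadjusted comorbidity tests, with no stated alpha and no deciding contrast

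*SAP*

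**What the plan says.** The primary objective in both documents is the impact of the comorbidity profile on response to biological therapy. To answer it, SAP 7.2 states that "two logistic regression models will be conducted". Protocol 7.4 plans the same: "two logistic regression models will be conducted. The dependent variable of the models will be the lack of response during the induction phase" in one, and loss of response during maintenance in the other. Neither outcome is placed first.

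On the terms in the models, SAP 7.2 says: "In both models independent variables will include all comorbidities, as well as sociodemographic and clinical variables as covariates". It then lists 29 candidate variables, 19 of them separate yes/no comorbidities. Every candidate is first compared between response groups, and "those variables whose p-value is lower than 0.1 are considered potential variables for performing a logistic regression analysis". After that, "The models will be assessed using stepwise automatic variable Wald entry (backward and forward) techniques"; no entry or removal levels are given.

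On reporting, "the results will be submitted for any statistically significant model, providing the following results: Odds Ratio, 95%CI, p-value, sensitivity and specificity". What makes a model significant is not defined.

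The Charlson index is summarised as a continuous variable in SAP 5.3 but is not among the candidates in SAP 7.2. Protocol section 4 speaks of developing a comorbidity scale, but no analysis section builds one.

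**The concern.** The comorbidity profile is never turned into one testable quantity. The plan does not say which comorbidity, score or joint test answers the objective, at what level, or what to conclude if the two models disagree. The only condition attached to significance concerns the whole model. Smoking, disease location or discontinuation of the biologic, all candidates in SAP 7.2, could satisfy it with no comorbidity effect present.

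A report could therefore present one odds ratio with p<0.05 from either model as the answer to the primary objective, and a reader could not tell it from chance. The selection procedure is not the only cause: the multiplicity remains if every comorbidity is forced into both models.

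**Working it through.** **Inputs from the documents.** Two models and 19 comorbidity items (SAP 7.2); screen at p<0.1 (SAP 7.2); 200 UC and 200 CD patients and 50% non-response (Protocol 7.1); primary non-response of up to 30% (Protocol section 4); at least 10 patients per variable and response category (Protocol 7.4).

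**Assumptions.** A two-sided 5% level, inferred only from the 95% intervals; stepwise removal at 0.05; all comorbidity prevalences.

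**1. The plan's own figure.** 10 events × 10 variables / 0.50 = 200 per disease, which reproduces the stated size. It is an events-per-variable rule and does not involve alpha.

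**2. Independence bound.** 19 × 2 = 38 tests.
- One model: 1 − 0.95^19 = 0.623.
- Both models: 1 − 0.95^38 = 0.858, with 38 × 0.05 = 1.9 false positives expected.
- With the 16 components of Protocol 6.4.4: 1 − 0.95^32 = 0.806.
- At the protocol's cap of 10 terms per model: 1 − 0.95^20 = 0.642.
- With correlated tests, the figure for 38 falls to 0.56 at correlation 0.5 and 0.28 at 0.8.

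**3. Simulation of the planned steps with no true effect.** N = 400 and 19 independent binary comorbidities; uncorrected chi-squared screen at 0.1, then backward Wald removal at 0.05. Primary non-response was analysed in all patients and loss of response in primary responders, as Protocol 6.4.5 defines it. Covariates were left out. There were 1,500 runs per cell, so the standard error is at most √(0.25/1500) = 0.013.

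| Prevalence of each comorbidity | Event rate in each phase | False comorbidity in a final model | Any univariable p<0.05 |
|---|---|---|---|
| 10% | 50% / 30% | 0.83 / 0.83 | 0.86 / 0.87 |
| 5% | 50% / 30% | 0.71 / 0.71 | 0.86 / 0.86 |
| 2% | 50% / 30% | 0.21 / 0.50 | 0.81 / 0.80 |
| Mixed, 0.2–6% | 50% / 30% | 0.27 / 0.37 | 0.65 / 0.74 |
| 1% | 50% / 30% | 0.01 / 0.15 | 0.58 / 0.75 |

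A second simulation of the same kind gave 19–69% at 2–5%, 22–30% with mixed prevalence, and 1–14% at 1%. At 0.5% the final-model rate was 0.00 (50% events) and 0.02 (30% events). The final-model rate drops in sparse data because the Wald test loses power there.

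**4. Without selection.** With all comorbidities forced into both models (latent correlation 0.2, four assumed prevalence sets from 0.25% to 10%), the rate was 0.21–0.61. After screening and backward removal on the same sets it was 0.18–0.54.

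**5. What a remedy can carry.** If loss of response is analysed in responders, 50% rates give 400 × 0.5 × 0.5 = 100 events and 30% rates give 400 × 0.7 × 0.3 = 84. The 10-per-variable rule then allows 10 or 8 variables, whereas 19 comorbidity terms alone need 190. One term per model fits. Even two tests both held at 0.025 give 1 − 0.975² = 0.049 if independent. For 38 item tests, Bonferroni (Holm's first step) is 0.05/38 = 0.0013, which gives 0.049 if independent.

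**The case against.** The strongest reply is that this is exploratory work. Protocol 7.3 says the analyses are primarily descriptive, and SAP 5.1 refers to the descriptive nature of the study. The study is a single-visit chart review sized without alpha, power or target effect. Strict familywise control is not obligatory in such a design, and that part of the reply stands. But the SAP 5.1 statement sits under the demographic and baseline description, Protocol 7.3 goes on to announce inferential testing of many endpoints, and SAP 7.2 is headed as the primary efficacy endpoint and carries no exploratory label.

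Second, a reader might infer that the plan declares the primary objective met when any one comorbidity is significant. The documents do not say so. The sentence on significant models is a reporting trigger, and the error rates above apply only if someone adopts that reading. The defect is that the plan leaves the reading open.

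Third, a reader might take 0.86 as the plan's error rate, or conclude that inflation is certain. Neither is supported. The figure assumes 38 independent tests, whereas the plan screens and selects, and Protocol 7.1 and 7.4 cap model size. Diabetes, solid tumour and liver disease are each split into two items, so the 19 items are not 19 distinct conditions. If the comorbidities are all very rare, the final models show little or no inflation.

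**Conclusion.** The point holds in a conditional form. SAP 7.2 states no alpha, ranks neither outcome, defines no deciding contrast or multiplicity control, and ties reporting to a criterion that covariates alone could meet.

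If an isolated p<0.05 is read as an impact of comorbidity, the chance of at least one false comorbidity in the final models is roughly 20–70% when prevalences are about 2–5% or mixed over 0.2–6%. It can fall to about 1–15% when every item is at 1%. Even at 1%, some univariable comparison reaches p<0.05 in more than half of runs, and those comparisons are tabulated (SAP Appendix 1, tables 14.3.1.1 and 14.3.1.3). The value 0.86 is only the independence upper bound.

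All of this rests on an assumed 5% level, assumed prevalences and event rates of 30% or 50%. The change should be made, but the design does not depend on it.

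**What to change.** In SAP 7.2:

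1. State a two-sided alpha of 0.05.
2. Report both models whether or not they are significant, and delete the significant-model condition. Appendix 1 already lists a regression table for each outcome (14.3.1.2 and 14.3.1.4).
3. Label the individual comorbidity odds ratios exploratory, and print a Holm-adjusted p-value beside each raw one. Count over all 38 candidate tests, including items dropped by screening or selection.
4. If a confirmatory statement is wanted, base it on one prespecified comorbidity term per model, such as the Charlson index already summarised in SAP 5.3. Apply Holm over the two models: the smaller p-value against 0.025 and, if that passes, the other against 0.05. Name the time point at which the index is scored, because Protocol 6.4.4 collects comorbidities both at diagnosis and at the study visit.

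A joint test of all 19 items is not the better choice here. It breaks the 10-per-variable rule, its ordinary likelihood-ratio form with Holm rejected in 0.08–0.14 of null simulations, and the permutation form that held 0.04–0.05 would need a scheme for handling covariates.

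The cost is SAP wording and a little programming, with no new data; the 200 + 200 sample size is unchanged because it does not depend on alpha. The downside is that an isolated association will less often count as a positive primary result.
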